#### **9.2.2.2. Allergic/Hypersensitivity Reactions**

All allergic or hypersensitivity reactions, including injection site reactions, will be reported by the investigator as either AEs or, if any serious criterion is met, as SAEs. Additional data, such as type of reaction and treatment received, will be collected on any AEs or SAEs that the investigator deems related to IP via an eCRF created for this purpose. IP should be temporarily interrupted in any individual suspected of having a severe or serious allergic reaction to IP (Section 8.1.2). IP may be restarted when/if it is safe to do so, in the opinion of the investigator. If IP is permanently discontinued, see Section 8.1.1 for procedures required in this situation.

#### **9.2.3. Adverse Event Monitoring with a Systematic Questionnaire**

Not applicable.

#### **9.2.4. Complaint Handling**

Lilly collects product complaints on investigational products and drug delivery systems used in clinical studies in order to ensure the safety of study participants, monitor quality, and to facilitate process and product improvements.

Study participants will be instructed to contact the investigator as soon as possible if he or she has a complaint or problem with the IP so that the situation can be assessed.

##### **9.2.4.1. Device Complaint Handling**

Any CGM device complaint should be reported via the manufacturer's instructions for device complaints. A 24-hour toll-free number will be provided to the investigative site personnel in the event that either personnel or study participants have questions regarding the device.

#### **9.3. Treatment of Overdose**

Study drug overdose (more than the specified number of injections) will be reported as an AE. In the event of an overdose, refer to the IB for LY3209590 and/or product label.

#### **9.4. Safety**

##### **9.4.1. Cardiovascular Events**

Deaths and nonfatal CV AEs will be adjudicated by a committee of physicians external to Lilly with cardiology expertise. The nonfatal CV AEs to be adjudicated include: myocardial infarction; hospitalization for unstable angina; hospitalization for heart failure; coronary

interventions (such as coronary artery bypass graft or percutaneous coronary intervention); and cerebrovascular events, including cerebrovascular accident (stroke) and transient ischemic attack.

#### **9.4.2. Electrocardiograms**

For each study participant, 12-lead digital ECGs, as well as single and triplicate safety ECGs, will be collected according to the Schedule of Activities (Section 2). Study participants must be supine for approximately 5 to 10 minutes before ECG collection and remain supine but awake during ECG collection. ECGs will be performed prior to collection of any blood samples.

ECGs will be interpreted by a qualified physician (the investigator or qualified designee) at the site as soon as possible after the time of ECG collection, and ideally while the study participant is still present, to determine whether the study participant meets entry criteria at the relevant visit(s) and for immediate study participant management should any clinically relevant findings be identified.

Digital ECGs will be electronically transmitted to a central ECG laboratory designated by Lilly. The central ECG laboratory will perform a basic quality control check (for example, demographics and study details) then store the ECGs in a database. At a future time, the stored ECG data may be overread at the central ECG laboratory for further evaluation of machine-read measurements or to meet regulatory requirements.

The machine-read ECG intervals and heart rate may be used for data analysis and report writing purposes unless an overread of the ECGs is conducted prior to completion of the final study report (in which case the overread data would be used).

#### **9.4.3. Vital Signs**

Sitting blood pressure (BP) and pulse rate will be measured using automated electronic sphygmomanometer according to the Schedule of Activities (Section 2). Vital sign measurements should be taken before obtaining an ECG tracing and before collection of blood samples for laboratory testing, at visits where required (see Schedule of Activities, Section 2). The participant should be required to sit quietly for 5 minutes before vital sign measurements are taken. An appropriately sized cuff (cuff bladder encircling at least 80% of the arm) should be used to ensure the accuracy of BP measurements. The arm used for the BP measurement should be supported at heart level. Blood pressure should be measured consistently using the same arm throughout the study. For each parameter (pulse rate, systolic BP, and diastolic BP), 3 measurements will be taken using the same arm; the recordings should be taken at least 1 minute apart, and each measurement of sitting pulse rate and BP will be recorded in the eCRF.

#### **9.4.4. Self-monitoring of Blood Glucose Using CGM**

A CGM system will be used in this study for self-measurement of plasma glucose equivalents. This system readings will be used for the purpose of monitoring study participant safety (hypoglycemia) and values shown by the system will be used for SMBG documentation. The system will proactively warn study participants of low blood glucose values. Study participants

should record all hypoglycemia related values read on the CGM device in the study diaries provided. Study participants with missing SMBG values may need to be retrained on the importance of SMBG monitoring.

Study participants will be instructed to take a pre-breakfast (fasting) SMBG reading every morning and 4-point SMBG measurements (consisting of fasting, pre-lunch, pre-dinner, and bedtime blood glucose measurements) once weekly throughout the study, and to record all results in diaries. Study participants will also measure FBG as needed to evaluate symptoms of hypoglycemia.

Study participants will be instructed to perform 6-point SMBG profiles over a 24-hour period on 2 nonconsecutive days during the 7-day period prior to visits indicated in the Schedule of Activities (Section 2). The 6-point profile consists of pre-meal and 2-hour postprandial SMBG measurements for the morning, midday, and evening meals in 1 day. Pre-meal measurements should be taken before the study participant begins eating the meal. Study participants should record their glucose measurements in their study diaries which are considered source documents and are to be returned to the investigator at each study visit. Values from the 6-point SMBG profiles will be transferred from the diaries and recorded on the eCRFs.

#### **9.4.5. Continuous Glucose Monitoring**

A CGM system will be provided to participating investigative sites. Study-specific training will be provided to investigative site personnel and study participants. The allowed range of the instrument recording is from 40 mg/dL to 400 mg/dL (2.2 mmol/L to 22.2 mmol/L) in the interstitial fluid (Gross et al. 2000). The results of the continuous monitoring will be unblinded to study participants and investigative site personnel and will be downloaded for transfer to Lilly or designee.

The study participants will be thoroughly trained on sensor insertion and usage, and CGM data/alarm interpretation during the randomization visit. Study participants should self-insert the first sensor at Visit 3 and initiate the CGM system under supervision of the trained site personnel. Thereafter, study participants will be provided with the necessary CGM supplies and will self-insert new sensors when alerted by the system.

The CGM device and sensor will monitor study participant glucose levels. Study participants will be unblinded to the real time CGM monitor readouts and alarms, so corrective action can be taken at the site regarding hypoglycemia prevention.

If problems occur with the CGM monitor or sensor, another sensor may be inserted or a replacement monitoring instrument may be used, as long as the CGM procedures and the subsequent visits continue to fall within the allowable time frames. A sensor or monitoring instrument provided specifically for this study must be used when replacing another sensor or CGM monitor.

#### **9.4.6. Laboratory Tests**

For each study participant, laboratory tests detailed in ([Appendix 2](#)) should be conducted according to the Schedule of Activities (Section 2).

With the exception of laboratory test results that may unblind the study, Lilly or its designee will provide the investigator with the results of laboratory tests analyzed by a central vendor, if a central vendor is used for the clinical trial.

Any clinically significant findings from laboratory tests that result in a diagnosis, and that occur after the study participant receives the first dose of IP should be reported to Lilly or its designee as an AE via eCRF.

#### **9.4.7. Immunogenicity Assessments**

Venous blood samples of approximately 10 mL will be collected to determine antibody production against LY3209590 as specified in the Schedule of Activities (Section 2). To interpret the results of immunogenicity, a PK sample will be collected at the same time points to determine the concentrations of LY3209590. All samples for immunogenicity should be taken predose when applicable and possible. In the event of drug hypersensitivity reactions (immediate or non-immediate), additional blood samples will be collected for anti-drug antibodies (ADA), PK and exploratory hypersensitivity analyses at the following time points, as close as possible to the onset of the event, at the resolution of the event, and 30 ( $\pm 3$ ) days following the event. Exploratory hypersensitivity samples may be analyzed for markers of basophil/mast cell activation (e.g., tryptase), immune complex formation (e.g., C3 levels) and cytokine release (e.g., IL-6) as appropriate for the clinical presentation. Instructions for the collection and handling of blood samples will be provided by the sponsor. The actual date and time (24-hour clock time) of each sampling will be recorded.

Immunogenicity will be assessed by a validated assay designed to detect ADA in the presence of LY3209590 at a laboratory approved by the sponsor. For the detection of anti-LY3209590 antibodies, study participant sera samples will be analyzed using a 3-tiered approach. All samples will be assessed in Tier 1 (screening) for possible presence of ADA. Samples found to produce a signal above or equal to the screening cut point will be assessed in Tier 2 to confirm specificity to LY3209590 (confirmation). Any samples confirmed as specific for LY3209590 will be reported as “detected”. All samples below the screening cut point in Tier 1 or not confirmed in Tier 2 will be reported as “not detected”. All “detected” samples in Tier 2 will be assessed in Tier 3 (titer assessment). In vivo laboratory indicators for glycemic control (blood glucose and HbA1c) will be utilized to detect a potential neutralizing effect of ADA against LY3209590.

Treatment-emergent antidrug antibodies (TE-ADA) are defined in Section [10.3.6](#). A risk-based approach will be used to monitor study participants who develop TE-ADA after treatment with LY3209590. Clinically significant TE-ADA will be defined as any TE-ADA at the follow-up visit with:

- A titer  $\geq 1:640$  or increasing ADA titer at follow-up visit.
- An association of TE-ADA with moderate to severe injection site reaction

Study participants who have clinically significant TE-ADA will be followed with ADA testing (every 3 months for up to 1 year after dose) until the titer reaches a plateau/decreases (if increasing) or remains the same/decreases (if high). A PK sample will continue to be collected at each time point at the investigator's discretion.

Samples will be retained for a maximum of 15 years after the last study participant visit, or for a shorter period if local regulations and Ethical Review Boards (ERBs) allow, at a facility selected by the sponsor. The duration allows the sponsor to respond to future regulatory requests related to the LY3209590. Any samples remaining after 15 years will be destroyed.

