Biomarker stored sample (plasma/serum)			X						X						X		X					X	X	X	X	
Ancillary Supplies/ Diaries/ Investigational Product																										
Study participant training/ education a		X																								Includes diabetes counseling, hypoglycemia (9.2.2.1), FPG profiles, diary completion, CGM sensor replacement
Study participant CGM Training			X																							

Procedure	Screening and Lead-in		Treatment Period																		Follow-up				ET	Notes a				
	1	2	3	4	5	6	7	8	9	10	11	12	13	14	15	16 b	17	18 b	19 b	20	21	22 b	801 c	802 c			803 c			
eCRF Visit Number	-2	-1	0	1	2	3	4	5	6	7	8	9	10	11	12	13	14	15	16 b	17	18 b	19 b	20	21	22 b	801 c	802 c	803 c		
Weeks																														
Visit window, days	±7	±3		±2	±2	±3	±2	±2	±3	±2	±2	±2	±2	±2	±3	±3	±3	±3	±3	±3	±3	±3	±3	±3	±3					
CGM Sensor Insertion			X																											Sensor inserted and system started by study participant under site personal supervision
Distribute CGM sensor f				X	X	X	X	X	X	X	X	X	X	X	X	X	X	X	X	X	X	X	X			X				
CGM data download				X	X	X	X	X	X	X	X	X	X	X	X	X	X	X	X	X	X	X	X		X	X	X			
Dispense supplies and diary		X	X			X			X				X			X		X			X	X				X				
IWRS	X	X	X	X	X	X	X	X	X	X	X	X	X	X	X	X	X	X	X	X	X	X	X		X	X	X	X		
Record diary and CGM data (including FPG g , hypoglycemia)			X	X	X	X	X	X	X	X	X	X	X	X	X	X	X	X	X	X	X	X	X		X	X	X	X		
Review diary and CGM data (including FPG g , hypoglycemia)				X	X	X	X	X	X	X	X	X	X	X	X	X	X	X	X	X	X	X	X		X	X	X	X		

Procedure	Screening and Lead-in		Treatment Period																			Follow-up			ET	Notes a					
	1	2	3	4	5	6	7	8	9	10	11	12	13	14	15	16 b	17	18 b	19 b	20	21	22 b	801 c	802 c			803 c				
eCRF Visit Number	-2	-1	0	1	2	3	4	5	6	7	8	9	10	11	12	13	14	15	16 b	17	18 b	19 b	20	21	22 b	801 c	802 c	803 c			
Weeks																															
Visit window, days	±7	±3		±2	±2	±3	±2	±2	±3	±2	±2	±2	±2	±2	±3	±3	±3	±3	±3	±3	±3	±3	±3	±3	±3	±3					
Record recent study drug dose/dose adjustment				X	X	X	X	X	X	X	X	X	X	X	X	X	X	X	X	X	X	X	X	X	X	X	X	X	X	X	
Dispense IP			X	X	X	X	X	X	X	X	X	X	X	X	X	X	X	X	X	X	X	X	X	X	X	X	X	X	X	X	

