### 7.4. Dosage Modification

Dosing will be individualized based on FBG. See [Appendix 7](#) and section [7.2.1.2](#) for details of dose modification.

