#### 9.1.2. Secondary Efficacy Assessments

- HbA1c change from baseline to Week 12
- Fasting glucose change from baseline to Weeks 12 and 32
- Insulin dose change from baseline to week 12 and 32

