### **10.3.6. Evaluation of Immunogenicity**

The frequency of antibody formation to LY3209590 will be determined. Treatment-emergent ADA are defined as those with a titer 2-fold (1 dilution) greater than the minimum required dilution if no ADAs were detected at baseline (treatment-induced ADA) or those with a 4-fold (2 dilutions) increase in titer compared to baseline if ADAs were detected at baseline (treatment-boosted ADA). For the TE ADA+ study participants, the distribution of maximum titers will be described.

The relationship between the presence of antibodies, antibody titers, and clinical parameters (for example, AEs, efficacy measures) may be assessed.

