## Appendix 7. Dosing Guidance

---

LY3209590 will be initiated at a loading dose [CCI] estimated to be comparable to the total daily basal insulin dose already administered prior to randomization. The [CCI] dose are shown in [Table BDCM.5](#). New dosing algorithms developed specifically for LY3209590 will be used by investigators for adjusting fasting glucose to achieve glycemic goals ([Table BDCM.6](#)). In situations where study participant safety is a concern or where dose adjustments have not had the desired therapeutic effect, investigators may only make adjustments to the dose of LY3209590 recommended by the dose-adjustment algorithm after consultation with Lilly.

At the time of site visit or telephone visit, the investigator will assess the study participant's glycemic control for the previous week and, if necessary, inform the study participant about any needed dose adjustment. The dose will be based on the study participant's blood glucose value. Adherence to the dosing algorithm provided for this study is required from Visit 3 (randomization) up to Visit 21 (Week 32, inclusive) and will be monitored periodically by the study team. Dose increases may be made no sooner than [CCI] (algorithm #1) or [CCI] (algorithm #2) [CCI] following the last dose increase. There should be no dose increase or decrease if at least [CCI], respectively, have not elapsed since the previous dose increase. Any deviations from this guidance must be approved by Lilly.

LY3209590 dose increase algorithm will be determined based on the mean of the FBG (determined from self-monitoring of blood glucose [SMBG]) [CCI]. Due to the long half-life of LY3209590, the change in fasting glucose response following dose adjustment may take several weeks to reach new level; therefore, less frequent dose adjustment is recommended to minimize prolonged variation in glycemic control.

The insulin dose may not be increased if [CCI]

[CCI]

[CCI]

[CCI]

[figure not shown]
Table BDCM.5 LY3209590 Loading Dose

CC

Table BDCM.6 LY3209590 Titration Algorithm

CCI

Leo Document ID = 918a14c6-c102-4f81-94a2-a4675ac3c540

Approver: PPD )  
Approval Date & Time: 31-Aug-2018 14:54:01 GMT  
Signature meaning: Approved

Approver: PPD )  
Approval Date & Time: 31-Aug-2018 16:06:36 GMT  
Signature meaning: Approved

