4.10.6. Antibodies

4.10.6.1. Anti-LY3209590 Antibodies

The sample to determine antibody against LY3209590 will be collected at protocol-specified visits. Treatment emergent antidrug antibodies (TEADA) can be subclassified as either treatment induced (baseline antibody level is not detected) or treatment boosted (baseline antibody level is detected):

- treatment induced response: a titer 2-fold (1 dilution) greater than the minimum required dilution (1:20) if the baseline level is not detected (i.e., titer less than the minimum required dilution)
- treatment boosted response: a 4-fold (2dilution) increase in titer compared to baseline if the baseline level is detected. For an example, 1:20 at baseline and 1:80 post baseline is treatment boosted.

The TEADA status will be determined by all postbaseline data. The number and percentage of patients with positive TEADA response any time after randomization including the treatment period and follow-up period will be summarized by treatment group.

A listing of anti-LY3209590 antibodies at each visit will be provided for the safety population. The listing will include anti-LY3209590 antibody status (detected/not detected), the titer for detected samples.

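### Blood glucose and HbA1c alone are insensitive indicators of ADA neutralization when LY3209590 dose is titrated on fasting glucose; LY dose by TE-ADA status should be read beside them

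*Protocol*

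**What the plan says.** **Detection of neutralization.** Protocol 9.4.7 sets out three assay tiers (screening, confirmation, titer) and names no neutralization assay. The functional assessment is one sentence: "In vivo laboratory indicators for glycemic control (blood glucose and HbA1c) will be utilized to detect a potential neutralizing effect of ADA against LY3209590". A PK sample accompanies each antibody sample to help interpretation, but concentration is not named as an indicator of neutralization.

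**Dose.** Protocol 7.4 states: "Dosing will be individualized based on FBG". Appendix 7 says that the LY algorithms "will be used by investigators for adjusting fasting glucose to achieve glycemic goals", with increases driven by mean self-monitored fasting glucose over a redacted window. Adherence to the algorithm is required through Week 32.

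**Dose data.** The Schedule of Activities has a row "Record recent study drug dose/dose adjustment". Protocol 9.1.2 lists "Insulin dose change from baseline to week 12 and 32" as a secondary efficacy assessment. SAP 4.8 summarizes dose descriptively and makes no treatment comparison, because the units differ between LY (mg) and degludec (units).

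**Antibody analyses.** Protocol 10.3.6 is optional: "The relationship between the presence of antibodies, antibody titers, and clinical parameters (for example, AEs, efficacy measures) may be assessed". Protocol 10.3.3.3 and 10.3.5 commit to examining the impact of detected ADA on LY PK or relevant PD parameters, and SAP 4.9 leaves PK/PD work to the PK/PD group. SAP 4.10.6.1 provides this: "The number and percentage of patients with positive TEADA response any time after randomization including the treatment period and follow-up period will be summarized". That summary is split by arm and accompanied by a listing. None of these sections names dose.

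**The concern.** In a titrated trial, fasting glucose is the controlled variable and dose is the controlling one. If antibodies remove part of the drug's effect, fasting glucose rises, the algorithm calls for more drug, and fasting glucose moves back toward goal. HbA1c follows to the extent that it depends on fasting glucose. Section 9.4.7 therefore looks for neutralization in the quantities that titration works to correct, and omits the quantity that would move.

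At stake is the interpretation of immunogenicity. Similar HbA1c in TE-ADA positive and negative participants could be taken as absence of neutralization even if the positive participants needed materially more drug. The HbA1c signal could weaken further if the comparison used the efficacy analysis set, because that set excludes data after rescue (SAP 4.1).

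**Working it through.** The plan gives no figure on this point, so there is none to reproduce. The check is a reading of the sections above, plus an illustration of how much signal remains in each measure.

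**Inputs from the documents.** Protocol 10.1 plans 100 completers per arm, so 2 × 100 = 200 on LY, and assumes an HbA1c SD of 1.1%. Tests are two-sided at alpha 0.10 (Protocol 10.3.1, SAP 4.1), giving a critical value of 1.645.

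**Assumptions not in the documents.** TE-ADA positive 10–30% of LY completers; log-dose SD 0.5–0.6; total HbA1c effect of the drug 1.5 percentage points; effect proportional to active drug; neutralized fraction q = 20% or 30%; share c of the lost effect restored by titration.

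**Model.** The same c is applied to both measures.
- Dose ratio, positive to negative: m = 1 + c × (1/(1 − q) − 1)
- Remaining loss of effect: 1 − m(1 − q) = q(1 − c)
- HbA1c difference: 1.5 × q(1 − c)
- Log-dose difference: ln(m)
- Power: Φ(δ/SE − 1.645) + Φ(−δ/SE − 1.645), with SE = SD × √(1/n₁ + 1/n₂)

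**Worked case, q = 30%, c = 80%.** The remaining loss is 0.30 × 0.20 = 0.06, so the HbA1c difference is 1.5 × 0.06 = 0.09. The dose ratio is 0.94/0.70 = 1.34, and ln(1.343) = 0.295.
- 10% positive (20 v 180): √(1/20 + 1/180) = 0.236. HbA1c SE = 0.259, ratio 0.35, power 12%. Log-dose SE at SD 0.6 = 0.141, ratio 2.08, power 67%.
- 30% positive (60 v 140): √(1/60 + 1/140) = 0.154. HbA1c SE = 0.170, ratio 0.53, power 15%. Log-dose SE at SD 0.5 = 0.077, ratio 3.82, power 99%.

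**Range.** Ranges run over 10–30% positive and, for dose, log-dose SD 0.5–0.6.

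| q | c | Dose ratio | HbA1c difference | Power, HbA1c | Power, dose |
|---|---|---|---|---|---|
| 30% | 0 | 1.00 | 0.45 | 54–84% | 10% |
| 30% | 50% | 1.21 | 0.225 | 22–38% | 39–81% |
| 30% | 80% | 1.34 | 0.09 | 12–15% | 67–99% |
| 20% | 0 | 1.00 | 0.30 | 32–55% | 10% |
| 20% | 50% | 1.125 | 0.15 | 16–23% | 22–45% |
| 20% | 80% | 1.20 | 0.06 | 11–12% | 36–76% |

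With no compensation the signal is in HbA1c, and dose shows only the 10% false-positive rate. At 80% compensation HbA1c power is close to that rate and the signal is in dose. Neither measure suffices across the range, so they need to be read together.

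**The case against.** **The protocol already plans ADA analyses against PK and PD.** This stands in part. Sections 10.3.3.3 and 10.3.5 are commitments, not options. Section 10.3.3.3 also relates LY dose and/or concentration to fasting glucose and HbA1c, and Table BDCM.2 lists dose-to-efficacy relationships as exploratory. A dose- or exposure-response model with ADA as a factor could separate neutralization from titration. Because SAP 4.9 hands this work to the PK/PD group, silence in SAP 4.10.6.1 does not show that it is unplanned. A reader might infer that the trial has no plan to relate antibodies to drug effect; the documents do not support that. What remains is that no section names dose in relation to ADA.

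**Efficacy measures in 10.3.6 could include dose,** since dose change is a secondary efficacy assessment. That is possible, but the analysis is optional and is not carried into the SAP.

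**Compensation may be limited.** This stands. A reader might infer that glucose and HbA1c are held constant by design and so carry no information. The LY titration table is redacted, and the visible text of Appendix 7 shows minimum intervals between increases, a fasting response that takes several weeks, and conditions under which dose may not rise. Titration also acts on fasting glucose only. Strong neutralization could still appear in HbA1c or rescue use.

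**Dose is a confounded measure.** This also stands. Dose reflects insulin resistance, and a higher dose may itself increase antigen exposure, so an association could run in the reverse direction. Adjusting for concurrent fasting glucose conditions on a post-baseline variable that both neutralization and titration affect. Dose should therefore be an additional indicator, not the main one.

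**Immunogenicity is exploratory.** That is correct, and it bounds the importance of the point.

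**Conclusion.** The concern holds as a question of sensitivity. Under fasting-glucose titration, blood glucose and HbA1c alone are weak detectors of partial neutralization, and the measure most likely to show it is recorded but not linked to antibody status. At 80% compensation on both measures, power is 12–15% for HbA1c against 67–99% for dose at 30% neutralization, and 11–12% against 36–76% at 20% neutralization. At 50% compensation the gap narrows to 22–38% against 39–81%, and to 16–23% against 22–45%. These figures rest on assumed values for TE-ADA frequency, log-dose SD, total HbA1c effect and compensation, and serve only as an illustration.

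The documents do not show that the trial will report absence of neutralization wrongly; that depends on what the PK/PD group does and on how the results are worded. The primary and secondary comparisons are unaffected.

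**What to change.** In Protocol 9.4.7 and SAP 4.10.6.1, add LY dose as an additional in vivo indicator of neutralization:

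- Express dose in mg and mg/kg on the log scale, as change from the first maintenance dose to Weeks 12 and 32.
- Compare it by TE-ADA status and by maximum titer, within the LY arms only. This also avoids the unit mismatch that ruled out a treatment comparison in SAP 4.8.
- Adjust for algorithm and baseline basal insulin dose. Use adjustment for concurrent fasting glucose as a sensitivity analysis only.
- Present fasting glucose, HbA1c and LY concentration by the same TE-ADA groups, and interpret the four together.
- State that the comparison is non-randomized and supportive, because dose also reflects insulin resistance and may itself influence antibody formation.

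The cost is a few sentences and one table. Dose, weight, titer, glucose, HbA1c and concentration are already collected, and no dosing rule changes.
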